### 12.0 Data Safety Monitoring

- The study will be reviewed annually by the Department of Anesthesia's DSMB. Minutes and outcomes from these meetings will be reported to the IRB as required.
- Information regarding Adverse Events is to be obtained and documented by the surgery center anesthesia attending and/or the study team member performing the data collection by questioning or examining the subject. All new complaints and symptoms (i.e., those not existing prior to signing of informed consent) will be recorded on the AE CRF. All AEs will be characterized in terms of their start and stop dates, start and stop times, intensity, action taken, relationship to research study, subject outcome and whether or not the AE led to an SAE.
- Adverse events will be recorded and reported to the Department of Anesthesia's Data Safety Monitoring Board and the IRB per policy.
- PHI will be managed in a manner that complies with institutional rules and regulations. There will be an enrollment log that links the study ID number to the participant. This log will be kept on a MUSC password protected server that can only be accessed by IRB approved study personnel.

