#### **Exclusion Criteria**

- Any contraindication to receiving regional anesthesia. This may include infection at the site of injection, allergy to local anesthetic, or pre-existing nerve injury.
- Patients undergoing hamstring graft or allograft for ACL
- Pre-existing infection at the site of injury
- Patients on chronic opioid treatments
- Pre-existing sensory or motor deficit in operative extremity
- Patients having a revision of previous ACL reconstruction
- Pregnant and/or lactating women
- Weighs less than 40kg

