#### **Baseline and Randomization**

After consenting and confirmation of meeting eligibility criteria, the participant will undergo the procedure as scheduled and as standard of care. The participant will be

randomized before they are anesthetized, as the block will be prepared and placed prior to the start of surgery.

If randomized to ACB-Only (Group A) the participant will receive the ACB block first. The injection site is prepared with a sterile solution, an injection of lidocaine is given to numb the area, then using ultrasound guidance a needle is inserted into the adductor canal at the mid-thigh where a catheter is placed to administer the long-acting anesthetic. Next, to maintain the blind, the participant will receive a skin wheal with lidocaine at the same location as Group B has the iPACK block placed.

Table 5. Post-Op Follow Up Assessments			
Outcome Measure	Instrument	Collected	
Pain Rating	Average pain, most pain, least pain from 0-10 POD Days 0-3		
Opioid Consumption	Number of pills taken in time period POD Days 0-3		
Physical Therapy	Range of Motion and terminal knee extension	Postoperative Visit 1 and 2	
Adverse Events	Adverse Events	Throughout enrollment	

If randomized to ACB + iPACK (Group B) the participant will be administered the ACB first as stated above and the iPACK block second. The iPACK block will be placed at the posterior part of the knee. The area will be numbed first using lidocaine, then using ultrasound guidance, a needle will be inserted in the popliteal fossa between the popliteal artery and the capsule of the knee.

Table 4. Baseline and Intraoperative Assessments		
Demographics		
Baseline		
Pre-op meds including opioids in past 24 hours		
Randomization		
Anesthesia intra-op data		
Surgical techniques		
Adverse Events		

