#### Follow-Up

The participant will be asked to provide their average pain score, worst pain score, and lowest pain score using a visual analog scale from 0-100 with 100 being the worst at various time points during the postoperative period. The first pain scores will be recorded before they leave the PACU on the day of the procedure. Beginning the following morning, the participant will receive a text message link sent by Twilio's secure server that opens a survey housed in RedCap. The first text message will arrive at 9:00 AM and will follow the schedule in Table 6.

They will receive a text message from a secure server asking the average pain questions as well as what medications they took for pain (including medication name, dosage, and frequency). The set of questions will state what time window (example:

12:00 AM midnight the night prior to 12:00 PM noon the same day) to consider when answering the questions. If the participant has been discharged from the hospital, they will answer these questions in the text message each day. If they are admitted to the hospital at this point in time, the information will be gathered from their chart for medications and asked verbally for pain scores. Range of motion and terminal knee extension will also be recorded at the in-person postoperative follow up visits.

If the participant is unable or unwilling to receive text messages, they will be provided a document to record their pain and medications for the pre-determined intervals so when a study member contacts them, they are able to relay their answers back accurately.

Table 6. Post-Op Follow Up Assessment Schedule			
Post-Op Day	Time of Text Message	Data Collection Time Period	
POD 0	Right before discharge	Waking up from surgery to discharge	
POD 1-AM	9:00 AM	Discharge to 11:59 midnight prior	
POD 1-PM	3:00 PM	12:00 AM midnight night prior to 12:00 PM noon same day	
POD 2-AM	9:00 AM	12:01 PM noon day prior to 11:59 AM midnight night prior	
POD 2-PM	3:00 PM	12:00 AM midnight prior to 12:00 PM noon same day	
POD 3-AM	9:00 AM	12:01 PM noon day prior to 11:59 AM midnight night prior	
POD 3-PM	3:00 PM	12:00 AM midnight prior to 12:00 PM noon same day	

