### 14.0 Risks to Subjects

- If a subject chooses not to participate the risk is the same since the interventions
  used are both standard of care at MUSC and will be offered regardless of study
  population.
- The interventions for both blocks include risks such as bleeding, infection, nerve damage, local anesthetic toxicity, allergic reaction, and/or damage to surrounding structures. These risks are rare.
- Subjects will be randomly assigned to receive either the adductor canal block, or adductor canal block with iPACK block. One group may prove to be less beneficial than the other.
- There is a risk of loss of confidentiality.

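### The adverse-event rule in section 12.0 covers symptoms that are new since consent and does not require worsening of a pre-existing symptom to be recorded

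*Combined protocol and SAP*

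**What the plan says.** Section 12.0 (Data Safety Monitoring) states what is to be recorded: "All new complaints and symptoms (i.e., those not existing prior to signing of informed consent) will be recorded on the AE CRF". The parenthesis defines a new symptom as one absent before consent was signed. The same section lists the details to be kept for each event, beginning "All AEs will be characterized in terms of their start and stop dates, start and stop times, intensity" and going on to action taken, relationship to the research, outcome and whether the event led to a serious one. It then sends adverse events to the department's monitoring board and the IRB under a policy that is not reproduced.

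Table 5 gives the collection period for adverse events as "Throughout enrollment" and does not define the term. Table 4 names adverse events among the baseline and intraoperative items, again without a definition. Section 14.0 names the hazards of both blocks as "risks such as bleeding, infection, nerve damage, local anesthetic toxicity, allergic reaction, and/or damage to surrounding structures" and calls them rare.

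**The concern.** Many adverse-event definitions have two limbs: something new, or something old that has become worse. Section 12.0 has only the first. That matters more here than in a trial of people with no prior complaint, because the blocks and the surgery are applied to a limb that is already injured. Consent is signed in the preoperative area on the day of surgery (sections 7.0 and 9.0), so any symptom from the injury that is still present that day predates consent and is not new under the rule.

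At stake is the completeness of what the monitoring board sees. A complaint that does not qualify as an adverse event gets no assessment of relatedness or seriousness and is not among the events that section 12.0 sends onward. If the second block, or either block, aggravated a knee that was already swollen or stiff, staff following the rule as written would not have to report it.

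**Working it through.** No arithmetic underlies the rule, and no stated figure depends on it. The check is whether any other part of the plan supplies what section 12.0 leaves out.

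**1. Is there a second rule?** No. Tables 4 and 5 name adverse events without defining them. Section 13.0 deals with withdrawal and section 14.0 with risks. Intensity is collected under section 12.0, but only for events that already count as adverse events, so it does not bring a worsened old symptom onto the form.

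**2. Which of the hazards named in section 14.0 would still be recorded as new?**
- Nerve damage: the exclusion criteria rule out "Pre-existing sensory or motor deficit in operative extremity", and the examples of contraindications include "allergy to local anesthetic, or pre-existing nerve injury". A deficit after the block would therefore be new.
- Infection: "Pre-existing infection at the site of injury" is an exclusion, and infection at the injection site is a listed contraindication. A later infection would be new.
- Toxicity and allergic reaction: new by nature.
- Bleeding and damage to surrounding structures: the needle sites are the mid-thigh and the popliteal fossa, both punctured after consent, so a hematoma there is a new complaint. The exception is a complication that shows itself only as more swelling, pain or stiffness in a knee that already had it.

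**3. What do the outcome data pick up?**

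| Symptom present before consent | Collected as an outcome? | Not covered |
|---|---|---|
| Pain | Yes. The Follow-Up section says "The participant will be asked to provide their average pain score, worst pain score, and lowest pain score using a visual analog scale"; the last window in Table 6 ends at noon on postoperative day 3 | Pain after day 3 |
| Stiffness | Yes, as range of motion and terminal extension at two visits: 7 to 21 days and 6 weeks (section 11.0) | Change between visits |
| Swelling, bruising | No | All of it |

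Taking 6 weeks as 42 days, the period with no pain collection before the last visit is 42 − 3 = 39 days. The wait from the last pain score to the first clinic visit is 7 − 3 = 4 days at the shortest and 21 − 3 = 18 days at the longest.

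Where an outcome does exist, it is a score. It carries no relatedness, action taken or seriousness assessment.

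**4. Is there a baseline against which to judge worsening?** In part. Section 11.0 uses preoperative pain and the preoperative difference in range of motion between legs as model covariates, so those two must be collected. The legible entries in Table 4 include no line for swelling or other operative-limb symptoms.

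**The case against.** The sentence sets a minimum. It says that new symptoms will be recorded; it does not say that nothing else may be, and the preceding sentence has staff question or examine the participant without limiting them to new complaints. The reporting policy is not in the document and may cover worsening. The serious block-related harms would nearly all qualify as new. Pain and motion are measured anyway, and some swelling is to be expected in both arms after knee surgery.

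Most of this stands, and it rules out several stronger readings that a reader might infer:
- *Worsening is never recorded.* The text does not forbid recording it, and early pain and loss of motion are captured as outcomes. The plan merely does not require worsening to be recorded as an adverse event.
- *The safety comparison between arms is biased towards no difference.* Section 11.0 plans no such comparison, the rule is the same in both arms, and there are no rates from which to show a bias.
- *All 82 participants enter with a symptomatic knee.* Eligibility requires a scheduled ACL reconstruction with one of two graft types; prior symptoms are a reasonable inference for some, but not a stated fact for all.
- *The monitoring board will not see worsened events.* With the policy unseen, this cannot be asserted.

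The objection does not remove the omission. A policy that might cover worsening is no substitute for a protocol sentence that defines new symptoms and stops there. Swelling, and pain after day 3, have no other route into the data.

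**Conclusion.** The point holds as a limited omission. Section 12.0 ties required recording to symptoms absent before consent, and no other part of the plan adds worsening. The remaining gap is marked worsening of a pre-existing symptom that is not being measured as an outcome at the time, chiefly swelling at any time and pain after postoperative day 3. Even where pain or motion is measured, relatedness and seriousness go unassessed.

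The size cannot be estimated from the plan, which gives no rates of preoperative symptoms or of worsening. The rule applies to all 82 planned participants, but how many have a prior symptom that could worsen is unknown. The conclusion assumes that some do, and that staff follow the sentence as written. The sample size, significance level and primary analysis are unaffected. This is a cheap improvement to safety capture and does not put the trial's main result in doubt.

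**What to change.** Extend the recording sentence in section 12.0 so that, besides new complaints, it covers *any pre-existing symptom that worsens in intensity or frequency after consent beyond what is expected after the surgery*. Add a line to Table 4 for operative-limb symptoms at baseline (pain, swelling, stiffness), so that new and worse can be told apart. Expected postoperative pain can stay in the pain endpoint alone.

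The cost is one clause, one line on the baseline form and slightly more events to record. The wording also asks staff to judge what is expected after this operation, and that judgement will vary between assessors unless the form gives brief guidance. No analysis or sample-size figure changes.

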### 13.0 Withdrawal of Subjects

- The participant has the right to voluntarily withdraw consent from the study at any time for any reason without prejudice to his/her future medical care by the physician or at the institution. For the occasional participant who withdraws consent, the date and reason for consent withdrawal should be documented. Participant data will be included in the analysis up to the date of the consent withdrawal.
- Investigators may stop a subject's participation in the study at any time if they decide it is in the subject's best interest. They may also do this if the subject does not follow the investigator's instructions.

### 14.0 Risks to Subjects

- If a subject chooses not to participate the risk is the same since the interventions
  used are both standard of care at MUSC and will be offered regardless of study
  population.
- The interventions for both blocks include risks such as bleeding, infection, nerve damage, local anesthetic toxicity, allergic reaction, and/or damage to surrounding structures. These risks are rare.
- Subjects will be randomly assigned to receive either the adductor canal block, or adductor canal block with iPACK block. One group may prove to be less beneficial than the other.
- There is a risk of loss of confidentiality.

### 15.0 Potential Benefits to Subjects or Others

There is a potential benefit that the subject's participation in the study may contribute to knowledge in this area of practice and may impact subject care in the future. The subject could also experience less post-operative pain.

# 16.0 Sharing of Results with Subjects

• Results will not be shared with participants or their families.

## 17.0 Drugs or Devices (if applicable)

- The drugs (all FDA approved for ACB blocks and iPACK blocks) used for both blocks will be prepared by the OR pharmacy under a sterile hood.
- The contents of the injectate will be based off of the participant's randomly assigned group.
- The pharmacist will not be blinded to the randomization.
- All drugs are FDA approved for use in adults and standard of care off label in children according to ASRA/ESRA guidelines.

